encompasses similar recovery mechanisms, we expect that benefits will be equally significant in these two populations. Expanding our study to outpatient population will also have clear benefits on enrollment, given that it will allow us to recruit TBI patients who did not receive direct care from our institution that would potentially otherwise be eligible.

III. OVERALL GOALS

We plan to conduct a phase II, 52 week, randomized, double-blind, placebo-controlled clinical trial that investigates the effect of Huperzine A on memory function in subjects who sustain moderate to severe traumatic brain injury. We will also explore the effects of Huperzine on transcranial magnetic stimulation (TMS)-induced neurophysiologic markers, EEG event related potentials (P50 and P300), seizure frequency/prevalence and incidence of adverse effects as secondary aims. Measures of mood, pain and subjective complaints of concussive symptoms, and length of time post-injury, will serve as covariates to address potential treatment confounders. The data generated from this study will be used to plan a subsequent phase II/III trial with Huperzine A.

IV. SPECIFIC AIMS

Primary Aim:

• To determine whether Huperzine A, as compared to placebo, has a differential effect on learning and memory functions after moderate to severe TBI. We hypothesize that the changes in mean scores on tests of learning and free recall as measured by the California Verbal Learning Test-II (CVLT-II) will be significantly greater after 12 weeks of treatment with Huperzine A in individuals with moderate to severe traumatic brain injury relative to those treated with placebo.

Secondary Aims:

- To determine whether administration of Huperzine A produces significant differences in neurophysiologic markers (as indexed by EEG event related potentials (P50 and P300) and TMS-indexed cortical excitability (cholinergic activity)) associated with cognition relative to a placebo. We expect that patients who receive Huperzine, as compared to placebo, will have decreased latency and increased amplitude for P50 and P300 and, in addition, they will have increased short latency afferent inhibition (as indexed by TMS measurement), thus indicating increased cholinergic activity and cognitive processing at 12 weeks post-enrollment.

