Variability in cognitive performance within and across assessments is common in both healthy and neurologically-impaired populations and may exceed two standard deviations in some cases. Practice effects are also common and generally attributable to increased familiarity with test materials, content, and process. To help mitigate these potential influences on test scores, Reliable Change Indices (RCI) [26] will be calculated at the 3 and 12 month reassessments. RCI's are determined by first subtracting the mean T2 - T1 change from the difference between the two testings for each individual, and then comparing it to 1.64 times the standard deviation of the difference. A difference of this magnitude is exceeded only 10% of the time (in either the positive or negative direction) if there is no real change. Applying a correction to change scores is particularly important in samples that include patients with severe TBI, as practice effects are magnified at higher levels of impairment and with shorter test-retest intervals [27].

All subjects will also undergo a neurophysiologic examination at the time of their baseline cognitive testing, and at 6 weeks, 12 weeks, 24 weeks and 52 weeks.

To control for the potential confounding effects of mood, pain and subjective distress on treatment, we will administer self-report measures in these areas at the time of enrollment. Scores on the Beck Depression Inventory, modified Brief Pain Inventory and British Columbia Post-Concussion Scale, obtained at baseline, will be used as covariates in our primary analysis. We will also use time post-injury as a covariate to control for the possible influence of length of time since injury on treatment outcome as spontaneous recovery will be more rapid in subjects enrolled early versus late, and because those enrolled later will be higher functioning at baseline.

Screening/Follow-up measures:

- Galveston Orientation Amnesia Test (GOAT): A series of 10 questions asked to a patient to help evaluate posttraumatic amnesia. The test is repeated at each visit, and is scored on a scale of 0 to 100. A patient is determined to be out of the amnesic state when the score exceeds 75 on three consecutive examinations.

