- Trail Making Test B: Part B of this test requires the patient to alternate between numbers and letters (i.e., 1-A-2-B, etc.) distributed in a spatial array [28, 29]. The task alternation aspect of Trail Making B increases its sensitivity to aspects of executive/frontal lobe function that are frequently altered in patients after TBI.
- Traumatic Brain Injury Quality of Life (TBI-QOL): The TBI-QOL [28] was developed as a comprehensive patient-reported outcomes (PRO) measurement system specifically for individuals with traumatic brain injury (TBI). It consists of 20 independent calibrated item banks and 2 uncalibrated scales that measure physical, emotional, cognitive, and social aspects of health-related quality of life. We will administer only the short form (6 questions) of the TBI-QOL Learning and Memory subscale.
- Ruff Neurobehavioral Inventory (RNBI): The RNBI [29] is a self-report instrument for assessment of a wide range of symptoms (cognitive, emotional, and physical), as well as

quality of life and daily functioning. It was designed to assess these areas in individuals who have recently been affected by an injury, illness, or other stressor. We will be administering the 24 question Postmorbid Cognitive Domain form of the RNBI.

Primary measure:

• CVLT-II: The California Verbal Learning Test provides a reliable measure of memory encoding and retrieval, which is often affected in patients with TBI. The California Verbal Learning Test second edition [30, 31] measures verbal learning and memory using a multiple-trial list-learning task. Sixteen words from 4 semantic categories are repeated for each of the five learning trials for list A. A distractor list (B) of 16 words from 2 of the same and 2 different semantic categories is then given. Short and long free and cued recall measures of list A are presented. There is also a recognition paradigm. Z-scores are computed for total learning trials 1-5 and all recall and recognition trials.

Covariates:

- Beck Depression Inventory (BDI): The Beck Depression Inventory (BDI) is a 21-item test presented in multiple-choice format that measures the presence of and the degree of depression in adults [32]. The BDI will be used to evaluate if mood is a confounder in this study.

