Changes in pupil diameter due a cognitive task are considered a reliable and sensitive index of the degree of cognitive load and resource demand to the task. We will record pupillary response, indexed as changes in pupil diameter, to two sets of tasks measuring cognitive performance: a low cognitive-load task vs. a high-cognitive load task. The first will consist of a set of simple stimuli presented to the patient in an organized and timely manner, which will then be recognized and named by the subject. The high-cognitive load task includes the presentation of a larger and more complex array of information for the subject to recall. Both sets of stimuli will be shown in a computer screen with a fixed interval between stimuli. Measurement of pupil diameter and reactivity will be conducted with a remote eye-tracker device. It consists of a high-resolution 17" computer screen placed in front of the subject's face that allows both stimuli display and pupil tracking through infrared diodes that generate reflection patterns of the user's cornea.

• Smooth pursuit eye movement (SPEM):

Eye movements will be recorded by an infrared-based eye-tracking device consisting of a high-resolution computer screen that will be placed in front of the subject's face at a 40cm distance. Subjects will be presented with a target stimulus that will move in a predetermined and consistent trajectory in the fixed background screen. We will measure different parameters based on this recording both at baseline and treatment completion, including eye and target velocity, index of target prediction, eye position error and intraindividual variability of eye error. Comparison of baseline to after-treatment measurements will be considered a reflection of cognitive changes.

X. STATISTICAL ANALYSIS

This is an exploratory phase II study with the intent of generating hypotheses for a confirmatory phase II/III trial, as well as in obtaining effect sizes and variances for sample size calculation for further confirmatory studies. The study is also designed to address the tolerability of Huperzine A in the moderate and severe TBI populations.

[figure not shown]

Figure 2: Effect size to total sample size ratio necessary for a powerful study

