In designing this exploratory study, we conducted a sensitivity analysis to obtain a sample size that would provide a reasonable effect size when comparing Huperzine A to placebo (Figure 2). This allows for detection of differences between the two treatments, to plan for further studies. Assuming a power of 80% and an alpha of 5%, we originally projected that a sample of 60 patients (30 patients in each group) would allow us to detect an effect size of 0.75 between the two groups (placebo and active). Given our prior studies in TBI and cognition, an effect size of 0.75 for the primary outcome measure (CVLT-II) is clinically meaningful, to compare two treatments.

The authorized addition of two self-report measures to our outcome assessment battery (i.e., Cognitive Function subscale from the Neurological Quality of Life Questionnaire and the Ruff Neurobehavioral Inventory) was expected to influence our original power estimate and required sample size. We calculated our effect size by estimating the upper and lower limits of the change score that would be demonstrated by the control group on our primary outcome measure (i.e., California Verbal Learning Test-II). This analysis showed that, to achieve an effect size of 0.75, the final sample size could vary between 15 and 39 subjects per group, given a mean difference

in performance between groups of 3.59 with a standard deviation of 3.30 to 5.13. In view of the variability in this estimate, we proposed that we would run 10 subjects, determine the degree of variability in performance and then adjust the sample size accordingly.

After enrolling 10 subjects, we assessed the data for an estimate of the average difference between groups (difference to baseline) on a ratio of 3:6. There was an estimated effect size of 1.19 between group A (M=4.67, SD=4.51) and group B (M=0.33, SD=2.50). Using a two sample t-test to detect the difference between groups, a minimum sample of 26 subjects will be required (13 per group).

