The anticipated loss to follow-up rate in this study is around 15% - like our other drug studies. To account for this loss-to-follow-up rate, a total of 15 patients per group (30 total) will be enrolled in the study. The primary analysis will be an intent-to-treat analysis that will include all randomized participants regardless of their compliance with the study treatment or follow-up schedule. Study subjects should have received at least 1 dose of study drug/placebo. All hypothesis testing will be conducted using $\alpha = 0.05$, two-sided.

To analyze the data, we will compare means using t-test and modeling the data with ANOVA for multivariate analysis controlling for baseline values and other important covariates. If necessary, non-parametric approaches including Mann-Whitney and Friedman's test for multivariate analysis will be used with data that are not normally distributed. We will also use Fisher's exact test for comparison of categorical variables such as proportion of adverse effects. In summary, we will use the following statistical tests according to our primary aims:

• Primary Aim: To determine whether Huperzine A, as compared with placebo, has a differential effect on learning and memory functions after moderate to severe TBI.

For this aim we will compare means using t-test (comparing differences (Week 12 – baseline) between the two groups) and modeling the data with ANOVA for multivariate analysis controlling for baseline values and other important covariates (for secondary analysis). If necessary, non-parametric approaches including Mann-Whitney and Friedman's test for multivariate analysis will be used with data that are not normally distributed.

• Secondary aim 1: To determine whether administration of Huperzine A produces significant differences in neurophysiologic markers (as indexed by EEG event related potentials (P50 and P300) and TMS-indexed cortical excitability (cholinergic activity)) associated with cognition, relative to a placebo.

For this aim we will also build models in which the main dependent outcome will be amplitude or latency measures (from P50, P300 and SAI) and the independent variables will be group, time and the interaction group*time.

• Secondary aim 2: To determine whether Huperzine A reduces the prevalence of post-traumatic seizures after moderate and severe TBI as compared to placebo

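### Section IX puts three baseline scores into the primary analysis, but Section X makes an unadjusted t-test primary and the covariate model secondary; no text says which prevails

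*Combined protocol and SAP*

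**What the plan says.** **Section IX (Outcome measures).** Baseline scores on the Beck Depression Inventory (BDI), the modified Brief Pain Inventory (BPI) and the British Columbia scale, "obtained at baseline, will be used as covariates in our primary analysis". The next sentence begins "We will also use time post-injury as a covariate" and attaches no primary or secondary label. Under its Covariates heading, the section lists exactly these four items. Of the first it says: "The BDI will be used to evaluate if mood is a confounder in this study".

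**Section III (Overall Goals).** The same four factors "will serve as covariates to address potential treatment confounders". The analysis they belong to is not named.

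**Section X (Primary Aim).** "For this aim we will compare means using t-test", applied to Week 12 minus baseline. The sentence then continues with "modeling the data with ANOVA for multivariate analysis controlling for baseline values and other important covariates (for secondary analysis").

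**Section X (general paragraph before the aims).** The t-test and the covariate model appear side by side, and neither is ranked.

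**Section X (sample size).** "Using a two sample t-test to detect the difference between groups, a minimum sample of 26 subjects will be required (13 per group").

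**Section X (opening).** "This is an exploratory phase II study with the intent of generating hypotheses".

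**The concern.** An unadjusted two-group t-test contains no covariates, so an analyst cannot follow both the Section IX sentence and the Primary Aim paragraph. Two results would be produced, and the text allows each to be called primary. If the label is settled only after both p-values are known, the stated two-sided 5% level no longer describes the procedure.

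Two smaller gaps go with this. Section X names baseline values but leaves its other covariates unspecified and does not refer to the Section IX list. Section IX does not say whether baseline CVLT-II belongs in the model it calls primary.

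Blinding does not close the gap. Section VIII keeps the lead-site statistician blinded until after the final analyses, but a choice between two p-values for group A against group B can be made without knowing which group is active.

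**Working it through.** **1. Which analysis was the trial sized for?** The inputs are the Section X interim figures: group A mean 4.67 (SD 4.51), group B mean 0.33 (SD 2.50), two-sided alpha 0.05. The 80% power is stated for the original projection and is assumed to carry over.

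- Effect size: d = (4.67 − 0.33) / √[(4.51² + 2.50²)/2] = 4.34 / 3.646 = 1.19, as stated.
- Noncentral t, 13 per group: df = 24, noncentrality 1.19 × √(13/2) = 3.03, power 82.9%.
- 12 per group gives 79.6%, so 13 is the smallest size that reaches 80%.

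The plan's 13 per group therefore reproduces as an unadjusted t-test. At d = 0.75, the effect that Section X calls clinically meaningful, the same test with 13 per group has 45.1% power.

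**2. The passages side by side**

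| Place | Unadjusted t-test | Model with covariates |
|---|---|---|
| IX, Outcome measures | not mentioned | primary (three scores); time since injury unlabelled |
| X, general paragraph | named, unranked | named, unranked |
| X, Primary Aim | named for the aim | secondary |
| X, sample size | basis of the calculation | not mentioned |

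**3. Cost of leaving the label open.** The literal conflict is between the t-test on change and a model for change with treatment and the three scores. The documents give no correlations. Assumed: 13 per arm; baseline to Week 12 correlation ρ of 0.5-0.9; the three scores jointly explaining 0-20% of the variance in Week 12 CVLT-II left after baseline. Rates come from simulation over that grid (100,000 null trials per setting and 60,000 per effect size).

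- Each analysis alone rejects in about 5% of null trials (0.049-0.052).
- P(either rejects) = P(first) + P(second) − P(both), which comes to 6.5-7.5%. With about 5% each, the two reject together in about 5 + 5 − 6.5 = 3.5% down to 5 + 5 − 7.5 = 2.5% of null trials.
- Disagreement on significance: 9.2-11.2% of trials at d = 1.19 and 11.6-18.1% at d = 0.75.

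**4. An optional alternative primary analysis.** This is an ANCOVA of Week 12 CVLT-II on treatment, baseline CVLT-II and time since injury. Treatment difference: d√[2(1 − ρ)]. Residual variance: (1 − ρ²)(1 − R²), where R² is the share explained by time since injury (assumed 0-20%). Residual df = 24 − 2 = 22. Chance covariate imbalance is averaged over.

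| d (t-test power) | R² | ρ = 0.5 | ρ = 0.7 | ρ = 0.9 |
|---|---|---|---|---|
| 1.19 (82.9%) | 0 | 89.2% | 85.2% | 81.2% |
| 1.19 | 0.1 | 92.0% | 88.6% | 85.0% |
| 1.19 | 0.2 | 94.6% | 91.8% | 88.8% |
| 0.75 (45.1%) | 0 | 52.5% | 47.7% | 43.6% |
| 0.75 | 0.1 | 56.8% | 51.7% | 47.4% |
| 0.75 | 0.2 | 61.8% | 56.5% | 52.0% |

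The largest loss against the t-test is 81.2 − 82.9 = −1.7 points. The largest gain is 61.8 − 45.1 = +16.7 points.

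**The case against.** The best defence is that the intention can be inferred. The statistical section puts the t-test under the Primary Aim, ranks the model second and sizes the trial on the t-test; the Section IX phrase is the outlier. This has force, and it is why the minimum fix keeps the t-test. It does not settle the matter, because no text gives Section X precedence and Section X's own general paragraph leaves the two unranked.

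A reader might infer several stronger criticisms that the documents do not support:

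- *That the covariates are undefined, or will be selected from the data.* Section IX lists four under a Covariates heading. The BDI sentence sits there and fits the stated purpose in Sections III and IX of dealing with mood as a confounder. No selection rule is described. What is missing is the link from Section X and a statement about baseline CVLT-II.
- *That the error rate rises further.* Adding baseline CVLT-II and time since injury takes the either-result rate to as much as 8.4%, but no section calls such a model primary.
- *That the fix removes the disagreement.* Both analyses stay planned and would disagree equally often. The fix settles which one is the headline. For the same reason, effect sizes for later trials will be available from both.
- *That the trial is mis-sized for an adjusted analysis.* With all five covariates, power moves by about −8 to +10 points against the t-test under the assumed ranges. Power is not the issue.

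It is also fair to say that the trial is exploratory and that each analysis alone holds its level.

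**Conclusion.** The contradiction between Section IX and the Primary Aim paragraph of Section X stands on the text alone and needs no assumption. Its consequence is modest: a nominal 5% error rate of about 6.5-7.5% if the label is chosen after the fact, and a headline that depends on that label in roughly one trial in ten at d = 1.19 and up to about one in six at d = 0.75. These sizes rest on the assumed correlation and explained variance in step 3 of the working, and on free choice between the two results. The documents leave that choice open but do not say that it will be made. The inconsistency is not fatal in an exploratory phase II study. It is worth correcting because Section X sets alpha at 0.05 for all hypothesis tests and intends the effect sizes and variances for planning confirmatory trials, whose planners need to know which analysis is the primary one.

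**What to change.** Name one primary analysis identically in Sections IX and X. Do this before unblinding and before any further comparison of outcome by group, including by coded group.

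**Minimum repair**
1. Keep the t-test on Week 12 minus baseline as primary.
2. In Section IX, relabel the analysis that uses the three scores as the secondary covariate-adjusted analysis.
3. Add the same ranking to the general paragraph of Section X.
4. In Section X, replace the open-ended reference to further covariates with the full list: baseline CVLT-II, BDI, modified BPI, post-concussion score and time since injury. State that all are entered regardless of observed imbalance.

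This costs wording in two sections, with no new data and no change in sample size.

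**Optional improvement.** Make the primary analysis the ANCOVA of step 4 of the working, with the t-test and the five-covariate model as named sensitivity analyses. All its variables are already collected. It uses 2 residual degrees of freedom. Under the assumed ranges its power changes by about −2 to +17 points, and the loss arises only if the baseline to Week 12 correlation is near 0.9 and time since injury is not prognostic.

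### The primary t-test on CVLT-II change does not adjust for baseline CVLT-II, and Sections IX and X disagree on whether the primary analysis is adjusted at all

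*Combined protocol and SAP*

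**What the plan says.** The Primary Aim paragraph of Section X (Statistical Analysis) says the trial will "compare means using t-test (comparing differences (Week 12 – baseline) between the two groups"). It then adds an ANOVA model "controlling for baseline values and other important covariates (for secondary analysis"). The sample size text in the same section rests on the same test: "Using a two sample t-test to detect the difference between groups, a minimum sample of 26 subjects will be required (13 per group"). All tests are two-sided at 0.05.

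Two other places read differently:

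- The general analysis sentence earlier in Section X names both methods with no ranking: "we will compare means using t-test and modeling the data with ANOVA for multivariate analysis controlling for baseline values".
- Section IX (Outcome measures) says that the Beck Depression Inventory, Brief Pain Inventory and British Columbia Post-Concussion Scale scores, "obtained at baseline, will be used as covariates in our primary analysis". It continues: "We will also use time post-injury as a covariate". Baseline CVLT-II is not in that list.

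Section VIII and Table 1 schedule CVLT-II at baseline for every subject. Section VIII describes randomization in permuted blocks of four or eight and names no stratification factor.

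**The concern.** A change score uses the baseline value, but only by fixing the slope of Week 12 on baseline at 1. The plan's own reasoning suggests a slope below 1. Section IX expects faster spontaneous recovery in subjects enrolled early and says that "those enrolled later will be higher functioning at baseline". Lower starters should then gain more. The same section expects larger practice effects at higher levels of impairment, which points the same way.

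If the slope is below 1, the change score carries noise that a fitted slope would remove. The arm that happens to start lower will also tend to show more improvement whatever the treatment does. With 13 evaluable subjects per arm, such imbalance is not rare. Section X also wants effect sizes and variances from this study to size the next trial, so precision matters even though the study is exploratory.

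**Working it through.** **Inputs from Section X.** Change of 4.67 (SD 4.51) in group A and 0.33 (SD 2.50) in group B; effect size 1.19; 13 evaluable per arm; two-sided 0.05; 0.75 described as clinically meaningful. The 80% power is stated for the original design and not restated for the revised sample size.

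**Assumed, because the documents do not give them.** The correlation rho between baseline and Week 12 CVLT-II, and the ratio k of the Week 12 SD to the baseline SD.

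**Step 1: reproduce the plan.** The SD is sqrt((4.51² + 2.50²)/2) = 3.646, so the effect is (4.67 − 0.33)/3.646 = 1.19. The noncentrality is 1.19 × sqrt(13/2) = 3.03. With 24 df this gives 82.9% power; 12 per arm gives 79.6%. So 13 per arm is the smallest number reaching 80%, and the plan's 26 is reproduced.

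**Step 2: residual variance after adjustment.** With the baseline SD set to 1:

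- variance of change = 1 + k² − 2·rho·k
- ANCOVA residual variance = k²(1 − rho²)
- R = second divided by first; for k = 1, R = (1 + rho)/2

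**Step 3: ANCOVA power.** The noncentrality is d·sqrt(n/2) / sqrt(R·(1 + 1/(2n − 4))), with 2n − 3 = 23 df. The factor 1 + 1/22 = 1.045 is the average cost of chance baseline imbalance. For d = 1.19, rho 0.5 and k = 1, this is 3.03/sqrt(0.75 × 1.045) = 3.43, which gives 90.7%.

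Power at 13 per arm with equal SDs (k = 1):

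| rho | d = 1.19 (t-test 82.9%) | d = 0.75 (t-test 45.1%) |
|---|---|---|
| 0.4 | 92.4% (+9.5) | 57.2% (+12.1) |
| 0.5 | 90.7% (+7.8) | 54.3% (+9.3) |
| 0.6 | 88.8% (+5.9) | 51.7% (+6.7) |
| 0.7 | 86.9% (+4.0) | 49.3% (+4.3) |
| 0.8 | 85.0% (+2.1) | 47.2% (+2.1) |
| 0.9 | 83.0% (+0.1) | 45.2% (+0.1) |

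Simulation with 20,000 trials per setting agrees. At d = 1.19 the gains are +7.6 points (rho 0.5), +3.8 (0.7) and +2.0 (0.8).

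**Step 4: unequal SDs, d = 1.19.**

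| k | rho 0.5 | rho 0.6 | rho 0.7 |
|---|---|---|---|
| 0.9 | +10.6 | +9.2 | +7.7 |
| 1.2 | +3.2 | +1.2 | −0.5 |
| 1.3 | +1.6 | −0.2 | −1.5 |

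The loss is bounded. The variance of change minus the ANCOVA residual variance equals (1 − rho·k)², which is never negative, so R cannot exceed 1. At R = 1, where the true slope is exactly 1, power is 81.1%, a loss of 1.8 points.

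**Step 5: chance imbalance.** The baseline mean difference has SD sqrt(2/13) = 0.39 baseline SD. The chance that it exceeds 0.5 SD in either direction is 2 × (1 − Φ(0.5/0.39)), about 20%. With equal SDs, a 0.5 SD imbalance shifts the expected change contrast by (1 − rho) × 0.5 baseline SD, or (1 − rho) × 0.5 / sqrt(2(1 − rho)) in SDs of change. That is 0.25 at rho 0.5, a third of the 0.75 target, and 0.16 at rho 0.8.

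**The case against.** The strongest reply is that nothing here is invalid. Over repeated randomization the t-test on change is unbiased and keeps its 5% level, and it is the test on which the trial was sized. A baseline-adjusted model is already planned as a secondary analysis, so an adjusted estimate will exist for planning the next trial. The study calls itself exploratory. All of this stands, and it makes the point one of efficiency and clarity.

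The second reply concerns size. A reader might infer that the trial gives up 8 to 9 points of power. The documents do not support a single figure: it needs rho near 0.5 and equal SDs at the two visits, and neither is given. Nor can one say that ANCOVA never loses. It loses about 0.9 points at rho 0.95 with equal SDs, and up to 1.8 in the worst case.

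The third reply is that Section IX already adjusts the primary analysis, and that time since injury captures much of the recovery gradient. This gives some protection, so it would be wrong to say that the plan has none. But Section IX conflicts with the Primary Aim paragraph and omits baseline CVLT-II. The unranked general sentence in Section X does not settle which model is primary.

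Finally, a reader might take the change score to be in raw points. Section IX mentions Z-scores, and Section X does not say which CVLT-II score is differenced. What can be said is that the change is unadjusted.

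**Conclusion.** The point holds as a recommendation on efficiency and on naming one primary model. It is not a finding of bias or of an invalid test. The Primary Aim paragraph makes baseline adjustment secondary. Section IX places other covariates in the primary analysis. Baseline CVLT-II is clearly in the primary test under neither.

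At 13 per arm with equal visit SDs, the gain from adjustment runs from about 9.5 points at rho 0.4 to nil at rho 0.9 for an effect of 1.19, and from about 12 points to nil for 0.75. For rho of 0.5 to 0.7, the gain is smaller, or a small loss, if the Week 12 SD exceeds the baseline SD, and larger if it is smaller. The expectations in Section IX favour a slope below 1, and so favour adjustment, but they do not quantify it. The shift from chance imbalance is conditional on the sample drawn. An imbalance above 0.5 SD arises in about one randomization in five.

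**What to change.** In the Primary Aim paragraph of Section X, make the primary test an ANCOVA of Week 12 CVLT-II with treatment arm and baseline CVLT-II as terms, two-sided 0.05. Keep the t-test on Week 12 minus baseline as the supporting analysis.

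Reconcile Section IX and the general sentence in Section X with that paragraph, so that one primary model is named. State whether the mood, pain, post-concussion and time-since-injury covariates belong to that model or to a secondary one, and which CVLT-II score is analysed.

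Date the change before unblinding. Group A and group B means from the first subjects have already been compared for the sample size, so record that the model was chosen on design grounds.

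The cost is a few sentences, one degree of freedom and, in unfavourable cases, about 1 to 2 points of power. No further subjects or data are needed.
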